4.2 Secondary efficacy endpoints

The secondary efficacy endpoints of this study are:

- CR rate, PR rate, and CT-based ORR as confirmed by an IRC as assessed by the modified Lugano Classification (Cheson, 2014) for Cohorts A and B (PTCL) based on CT and after at least 8 weeks from the first assessment by Olsen Criteria (Olsen, 2011) for Cohort C (TMF).
- ORR-2 confirmed by Investigator assessment as assessed by the modified Lugano Classification (Cheson, 2014) for Cohorts A and B (PTCL) and after at least 8 weeks from the first assessment by Olsen Criteria (Olsen, 2011) for Cohort C (TMF).
- DOR as assessed by the modified Lugano Classification (Cheson, 2014) for Cohorts A and B (PTCL) and after at least 8 weeks from the first assessment by Olsen Criteria (Olsen, 2011) for Cohort C (TMF) based on IRC assessment.
- Assessment of non-compartmental PK parameters including C_{max} , AUC, volume of distribution at steady state (V_{ss}), half-life ($t_{1/2}$).
- Incidence of subjects who develop anti-drug antibodies (ADA) during treatment in blood and their neutralizing potential.
- QOL as measured by European Quality of Life 5-Dimensional (EQ-5D) for Cohorts A and B, and by Skindex-29 for Cohort C.

4.3 Exploratory endpoints

Final Analysis Statistical Analysis Plan (SAP)

- █ [REDACTED]
- █ [REDACTED]
- █ [REDACTED]

[REDACTED]

- █ [REDACTED]
- █ [REDACTED]
- █ [REDACTED]

4.4 Safety endpoints

The safety endpoints of this study are:

- Number and frequency of treatment-related adverse events (AEs).

Final Analysis Statistical Analysis Plan (SAP)

5 SAMPLE SIZE AND POWER

Refer to protocol section 8.8.1.

6 ANALYSIS POPULATIONS

6.1 Full analysis set (FAS)

The full analysis set (FAS) following the intent to treat (ITT) principle will consist of all subjects who received at least one dose of AFM13.

The FAS will be the primary population for all efficacy related endpoints and the primary objective. A sensitivity analysis for all subjects who received at least one dose of AFM13 and had at least one post-baseline efficacy assessment will be conducted to support the results of the primary analysis.

6.2 COVID analysis set

The COVID analysis set will include all subjects from the FAS excluding subjects who ended the treatment due to COVID-19 before the first post-baseline efficacy assessment. [REDACTED]

6.3 Safety set (Safety)

The safety set will consist of all subjects who received at least one dose of AFM13 and had at least one post-baseline safety assessment (where the statement that a subject had no AE on the AE eCRF constitutes a safety assessment).

The safety set will be the primary population for all safety related endpoints.

6.4 Per protocol set (PP)

The PP set will consist of all subjects in FAS who did not have any major protocol deviations. To support the results of the primary analysis on the FAS, the primary analysis will be repeated using PP Set.

6.5 Pharmacokinetic set (PK)

The pharmacokinetic set (PK) set consists of all subjects who have at least received one dose of study drug and have at least one post dose PK measurement.

6.6 Protocol deviations and exclusions from analysis sets

Key (defined as deviation that may impact the safety or integrity of the study) and non-key protocol deviations to be collected during the study are listed and described in the Protocol Deviation Criteria Determination document. This document indicates also among all the deviations which ones may be major (a major deviation

Final Analysis Statistical Analysis Plan (SAP)

[figure not shown]
excludes a subject from the PP population). There is no relationship between key/non-key and major/minor deviations as a key deviation can be considered as minor for the statistical analyses.

All deviations will be reviewed at the Classification Meeting through clinical review input provided by Sponsor and will be classified as major or minor. Then, exclusions of subjects from analysis sets will be identified. The following sources of information will be used to support the inclusion or exclusion of subjects in analysis sets:

- Supportive subject listings, provided by the ICON lead statistician ahead of the Classification Meeting, based on data recorded on the eCRF.
- Protocol Deviation Logs, provided by ICON Medical.

[figure not shown]

**Final Analysis
Statistical Analysis Plan (SAP)**

[figure not shown]

**Final Analysis
Statistical Analysis Plan (SAP)**

[figure not shown]

**Final Analysis
Statistical Analysis Plan (SAP)**

**Final Analysis
Statistical Analysis Plan (SAP)**

Final Analysis Statistical Analysis Plan (SAP)

8 STATISTICAL METHODS

8.1 General statistical conventions

All statistical procedures will be completed using SAS version 9.4 or higher.

Unless otherwise stated, all statistical testing will be two-sided and will be performed using a significance (alpha) level of 0.05. Two sided 95% confidence intervals (CI) will be provided when relevant.

Continuous variables will be summarized using descriptive statistics, including number of subjects (n), mean, median, standard deviation (SD), minimum (Min) and maximum (Max).

For categorical variables, summaries will include counts of subjects and percentages. Percentages will be rounded to one decimal place.

For summary purposes, baseline will be defined as the last available pre-dose value.

[REDACTED]

All subject data, including those derived, will be presented in individual subject data listings. Unless otherwise stated, unscheduled visit results will be included in date/time chronological order, within subject listings only. All listings will be sorted by cohort, subject number, assessment date/time and visit. Patient's sex and age will be also stated on each listing. Unless otherwise stated, data listings will be based on FAS.

Subjects who were screened and have signed the informed consent form (ICF) but did not receive any treatment will be listed including reason for screen failure or not being treated and any SAE (this will be recorded in the medical history). These subjects will not be part of any summary table except for summarizing disposition.

Final Analysis Statistical Analysis Plan (SAP)

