5.4 Description of Study Interventions and Assessments

Details of the procedures to be followed for specified study assessments are provided. During the study, additional assessments may be carried out as clinically indicated.

[REDACTED]

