Where a subject has the same adverse event, based on SOC and/or PT, reported multiple times, the subject will only be counted once at the SOC and/or PT level in adverse event frequency tables.

When reporting adverse events by severity, in addition to providing a summary table based on the event selection criteria detailed above, summary table will also be provided based on the most intense event regardless of the relationship to study treatment.

Final Analysis Statistical Analysis Plan (SAP)

IRR will be summarized by visit and cohort. But IRRs are collected during the study without being linked to a specific visit. Consequently, the following rule will be used to assign the IRRs to a visit:

If study drug administration at Cycle X Day Y \leq IRR start date/time \leq study drug administration at Cycle X Day Y + 24 hours then the visit is assigned to Cycle X Day Y; else visit is assigned to Unscheduled (Unscheduled visit should be also included in the “by visit” table).

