8.7.2 Clinical laboratory evaluations

For the purposes of summarization in both the tables and listings, all laboratory values will be presented in standard units.

Laboratory results will be graded by NCI CTCAE version 5.0. For the tests without grading, only the classification according to normal ranges will be done.

Hematology (including coagulation), chemistry and urinalysis will be summarized by cohort, visit and parameters in each category.

If a lab value is reported using a nonnumeric qualifier eg, less than (<) a certain value, or greater than (>) a certain value, the given numeric value will be used in the summary statistics, ignoring the nonnumeric qualifier. This will be explained in the footnotes of the respective outputs.

Descriptive statistics for actual measurement and change from baseline at scheduled visits will be performed.

Urinalysis parameters will be also summarized by frequency counts by cohort and for each scheduled visit for nonnumeric parameters.

Shift tables for CTCAE grades and normal ranges from baseline to each visit and to worst post-baseline visit will be presented.

All laboratory tests will be listed. A separate listing for abnormal lab values (\geq Grade 3, and low/high values) will be presented.

Liver and renal events

The subjects with liver events at any post-baseline visit will be summarized and listed for the following categories:

- ALT or AST $> 3 \times$ upper limit of normal (ULN).
- Alkaline phosphatase (ALP) $> 2 \times$ ULN.
- Total bilirubin $> 2 \times$ ULN.
- (ALT or AST $> 3 \times$ ULN) and total bilirubin $> 2 \times$ ULN and ALP $> 2 \times$ ULN.

Final Analysis Statistical Analysis Plan (SAP)

- LDH > 2 x ULN.
- Albumin < lower limit of normal (LLN).

Glomerular filtration rate (GFR) in mL/min/1.73 m² will be summarized and listed at each visit and to worst post-baseline visit with the following categories: <15, [15-30[, [30-45[, [45-60[, [60-90[and ≥ 90.

GFR values will be derived using Chronic Kidney Disease Epidemiology Collaboration (CKD-EPI) equation:

$$GFR = 141 \times MIN \left(\frac{Creat}{K}, 1 \right)^\alpha \times MAX \left(\frac{Creat}{K}, 1 \right)^{-1.209} \times 0.993^{Age} \times 1.018 [if Female] \times 1.159 [if Black or African American]$$

where

Creat is serum creatinine in μmol/L

K is 61.9 for females and 79.6 for males

α is -0.329 for females and -0.411 for males.

[REDACTED]

[REDACTED]

[REDACTED]

[REDACTED]

[REDACTED]

[REDACTED]

[REDACTED]

[REDACTED]

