8.7.6 Electrocardiograms

Shift tables from baseline (Normal/Abnormal-clinically significant/Abnormal–not clinically significant) to each time point and to worst post-baseline ECG interpretation will be summarized for ECG interpretation data. Descriptive statistics for actual and changes from baseline will be displayed for heart rate (msec), QRS interval (msec), RR interval (msec), PR interval (msec), QT interval (msec), QTc interval (msec).

ECG data will be listed overall and a separate listing for any clinically significant finding in ECG values will be provided.

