8.7.7 ECOG performance status

Shift table for performance status (0 to 5 grades) of subjects from baseline to the worst post-baseline visit will be presented by cohort.

A listing of the performance status of subjects will be provided by visit.

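### As readable, the SAP's listings-only default for unscheduled results is not lifted for the worst-post-baseline laboratory, ECG and ECOG tables, which may therefore understate the worst value

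*SAP*

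**What the plan says.** SAP 8.1 (General statistical conventions) gives the default for unscheduled data: "Unless otherwise stated, unscheduled visit results will be included in date/time chronological order, within subject listings only". The proviso at its start means that a later section can override it.

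The tables at issue come later in the SAP:

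- **Laboratory, 8.7.2.** "Shift tables for CTCAE grades and normal ranges from baseline to each visit and to worst post-baseline visit will be presented". GFR categories are likewise summarized at each visit and at the worst post-baseline visit.
- **Liver events, 8.7.2.** "The subjects with liver events at any post-baseline visit will be summarized and listed for the following categories".
- **ECG, 8.7.6.** Shifts from baseline to each time point and "to worst post-baseline ECG interpretation will be summarized for ECG interpretation data".
- **ECOG, 8.7.7.** A shift table "from baseline to the worst post-baseline visit will be presented by cohort".

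None of these sentences mentions unscheduled results. Protocol 5.4 expects such results to exist: "During the study, additional assessments may be carried out as clinically indicated".

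**The concern.** Keeping unscheduled results out of by-visit means and by-visit shifts is sensible, because they belong to no nominal visit. A worst-post-baseline table has a different purpose: it reports the most extreme value observed in each subject. An assessment added because it was clinically indicated may be the one that holds that extreme.

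Suppose a subject has Grade 0 at baseline, Grade 1 at the scheduled draws on either side, and Grade 3 at an unscheduled draw in between. Under the default, the worst-grade table shows a shift from 0 to 1. With all values used, it shows 0 to 3.

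Safety and tolerability is a secondary objective, the study has no control arm, and SAP 8.7 plans no safety tests. The tabulated counts are therefore the safety result that a reader takes away, and no comparator shares the omission.

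**Working it through.** The documents state no figure on this point, so there is nothing to reproduce. The check compares the text and then establishes the direction of the effect.

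**Step 1: does any readable section override the default?**

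| Table | SAP section | Unscheduled results addressed? |
|---|---|---|
| Laboratory shift to worst post-baseline | 8.7.2 | No |
| GFR category, worst post-baseline | 8.7.2 | No |
| Liver events, any post-baseline visit | 8.7.2 | Not named; the scope can be read either way |
| ECG interpretation, worst post-baseline | 8.7.6 | No |
| ECOG, worst post-baseline | 8.7.7 | No |

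So the default applies to four tables on its literal terms and is ambiguous for the liver table.

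**Step 2: direction.** Let S be a subject's scheduled post-baseline values and U the unscheduled ones. For a grade, where higher is worse, max(S) ≤ max(S ∪ U). For GFR, where lower is worse, min(S) ≥ min(S ∪ U). Dropping U therefore leaves the subject's worst value unchanged or makes it look milder. The count of subjects at or beyond any threshold cannot rise.

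**Step 3: size, as an illustration only.** The documents give neither of the two inputs needed, so both are assumed:

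- The true share of subjects with a Grade ≥3 value is taken as 10%.
- u, the share of those subjects whose Grade ≥3 values all come from unscheduled tests, is taken from 0 to 50%.

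The cohort maxima, 103 for Cohort A and 22 for Cohort C, are from the Protocol synopsis. The formulas are:

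- Rate shown = 10% × (1 − u)
- Expected count shown at N = 103: 103 × 0.10 × (1 − u) = 10.3 × (1 − u)
- Chance that at least one such subject is missing from the Grade ≥3 cells = 1 − (1 − 0.10u)^N

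| Assumed u | Count shown, N = 103 | Rate shown | Chance ≥1 missing, N = 103 | Chance ≥1 missing, N = 22 |
|---|---|---|---|---|
| 0 | 10.3 | 10.0% | 0% | 0% |
| 10% | 9.3 | 9.0% | 64.5% | 19.8% |
| 25% | 7.7 | 7.5% | 92.6% | 42.7% |
| 50% | 5.2 | 5.0% | 99.5% | 67.6% |

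If u is 0, nothing is lost. The table shows how the result depends on u and does not estimate the loss in this trial.

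**The case against.** **Unseen text may settle it.** Part of 8.1 is redacted just before the paragraph that holds the rule. The content of SAP section 7, including 7.1 on derived variables, is not shown, and a worst post-baseline value is a derived variable. Either place could define it to include unscheduled results. This stands, and it limits the point to the readable text.

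**The SAP's own wording can favour inclusion.** In 8.7.2 the restriction to scheduled visits is written out for some outputs: "Descriptive statistics for actual measurement and change from baseline at scheduled visits will be performed", and similarly for the urinalysis counts. The shift and liver tables carry no such words. If 8.1 already removed unscheduled data everywhere, the restriction would be redundant. A strict reading of 8.1 would also sit badly with efficacy. Appendix A labels off-window disease assessments as unscheduled, yet best overall response in 8.6.2 ranks all of a subject's response assessments. So 8.1 may be meant only as a convention for by-visit presentation. This is a fair reading, but it conflicts with the word *only* in 8.1, and two programmers could build different tables from the same text.

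**Other outputs catch the values.** Protocol 5.4.7 and 5.4.8 have clinically significant laboratory and ECG changes recorded as adverse events. SAP 8.7.1 tabulates treatment-emergent events by maximum severity and at Grade ≥3. Laboratory values of Grade ≥3 and clinically significant ECG findings have their own listings. None of this depends on a scheduled visit, so the mitigation is real but partial. A listing gives no count or shift, and the adverse event route depends on the Investigator's judgement of clinical significance.

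**Stronger readings the documents do not support:**

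- *That the infusion-reaction table shows the authors lift the rule where they want to.* SAP 8.7.1 does say "Unscheduled visit should be also included in the" by-visit table. There, however, the word labels reactions that do not start within 24 hours after an infusion. It does not refer to results from an unscheduled visit, so it says little about laboratory, ECG or ECOG data.
- *That a share lost can be worked out from the dosing interval and an assumed duration of abnormality.* The laboratory schedule is redacted. Such a calculation would also need every abnormality missed at scheduled draws to have been caught by an unscheduled one, and every-other-week dosing is open only to a select group of responders after Week 16.
- *That ECOG is assessed because toxicity is suspected.* It is a performance score, and nothing in the documents says so. ECOG belongs here only because the same inclusion rule should cover it.

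**Conclusion.** The point holds as a defect in the readable text with a known direction and an unknown size. Followed literally, SAP 8.1 keeps clinically indicated unscheduled values out of the worst-post-baseline laboratory, GFR, ECG and ECOG tables, and possibly out of the liver-event table. Those tables may then understate a subject's worst value and can never overstate it.

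A reader might infer that severity *is* understated across the safety report. The documents do not show that. The exclusion is not certain given the unseen text, the loss is zero if no worst value is unscheduled-only, and the adverse event tables and listings are unaffected. On the assumed 10% true rate, the rate shown runs from 10% down to 5% as u goes from 0 to 50%.

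Confidence is moderate. The conclusion rests on no exception being present in the redacted part of 8.1 or in section 7. The primary endpoint is not affected.

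**What to change.** Add one sentence to SAP 8.1 and repeat it in 8.7.2, 8.7.6 and 8.7.7: *By-visit descriptive statistics use scheduled visits only; every worst-post-baseline and any-post-baseline derivation (laboratory CTCAE and normal-range shifts, liver events, GFR category, ECG interpretation, ECOG) uses all post-baseline values, scheduled and unscheduled.* If the redacted part of 8.1 or section 7 already says this, the sponsor need only confirm it and add a cross-reference at each table.

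The cost is wording and a programming flag. Unscheduled results are already due to be listed, so no new data are needed. Some worst-grade counts may become less favourable.

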8.2 Subject disposition

Subject disposition information will be summarized by cohort and overall. The following number and percent of subjects will be summarized:

- Subjects who are pre-screened.
- Subjects who are screened.
- Subjects who are screen failures.
- Subjects enrolled for the treatment period but not treated.
- Subjects included in the FAS.
- Subjects included in the FAS and have at least one post-baseline efficacy assessment.
- Subjects included in the COVID analysis set.
- Subjects included in the safety set.
- Subjects included in the per protocol set.
- Subjects included in the PK set.
- Subjects who discontinued the treatment phase.
 - o Subjects impacted by COVID-19 who discontinued the treatment phase.
 - o Subjects affected by COVID-19 who discontinued the treatment phase.
- Subjects who performed the final study visit.
- Subjects who remained in response at the end of the treatment.
- Subjects who did not remain in response at the end of the treatment.
- Subjects who completed the study.
- Subjects who discontinued the study.

The number of subjects in FAS will be used as the denominator for the percentage calculation. Subject disposition and subject classification in each analysis population will be listed.

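### SAP 8.2 divides every disposition row by the treated set, so the four pre-treatment rows print figures that are not proportions and, for two of them, can exceed 100%

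*SAP*

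**What the plan says.** SAP 8.2 introduces its list with "The following number and percent of subjects will be summarized", by cohort and overall. The list opens with four rows that precede treatment: "Subjects who are pre-screened", "Subjects who are screened", "Subjects who are screen failures" and "Subjects enrolled for the treatment period but not treated". The analysis sets, treatment discontinuation and study completion follow. The section then closes the matter of percentages with one rule and no exception by row: "The number of subjects in FAS will be used as the denominator for the percentage calculation".

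SAP 6.1 defines the FAS as the set that "will consist of all subjects who received at least one dose of AFM13". Protocol 8.1 defines it the same way.

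SAP 8.1 confirms that people who consented and were screened but never dosed do enter this table. After saying they will be listed with the reason, it adds: "These subjects will not be part of any summary table except for summarizing disposition".

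Protocol 3.3, 5 and 5.1.1 describe a two-stage entry. CD30 testing comes first, under its own consent. Main screening follows under a second consent, and the first dose comes after that.

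**The concern.** A percentage needs a denominator that contains its numerator. The FAS is the last and smallest group in the entry sequence, so it cannot play that role for the stages before it. Two of the four rows are larger groups that contain the FAS, and the other two lie wholly outside it.

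This matters mildly because entry depends on a central CD30 result. In a single-arm study, the share of tested patients who qualify and are treated tells the reader how selected the sample is. By SAP 8.1, disposition is the only summary table that includes untreated subjects, so no other planned table would show that share as a correct percentage.

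**Working it through.** The plan states no screening or disposition figure, so there is nothing to reproduce. The check is set logic plus an illustration.

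**Inputs from the documents**
- Denominator for every row: number in the FAS (SAP 8.2).
- FAS: dosed subjects only (SAP 6.1, Protocol 8.1).
- Order of stages: pre-screening, screening, first dose (Protocol 5).
- Illustrative FAS size: the planned maximum of 150, which equals the cohort maxima 103 + 25 + 22 (Protocol synopsis).

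**Assumptions (not in the documents)**
- s, the proportion of screened subjects who fail main screening: 10% to 60%.
- Loss at pre-screening: 20% or 50%.
- Everyone who passes screening is treated. Counts are rounded up to whole subjects.

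**Step 1: rows that contain the FAS.** The FAS is a subset of those screened, who are a subset of those pre-screened. So screened/FAS and pre-screened/FAS are each at least 100%, with equality only if nobody in that row goes untreated. Under the assumptions, screened/FAS = 1/(1-s).

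**Step 2: rows outside the FAS.** A screen failure is never dosed, so the row prints failures/FAS = s/(1-s), which is the true rate multiplied by 1/(1-s). At s = 20%: 0.20/0.80 = 25%. The row exceeds 100% only when failures outnumber treated subjects, that is, when s is above 50%.

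With FAS = 150:

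| Assumed s | Screened | Failures | Screened row as printed | Failure row as printed | Failures / screened |
|---|---|---|---|---|---|
| 10% | 167 | 17 | 111.3% | 11.3% | 10.2% |
| 20% | 188 | 38 | 125.3% | 25.3% | 20.2% |
| 30% | 215 | 65 | 143.3% | 43.3% | 30.2% |
| 50% | 300 | 150 | 200.0% | 100.0% | 50.0% |
| 60% | 375 | 225 | 250.0% | 150.0% | 60.0% |

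The pattern is the same at cohort size. For 22 treated and s = 20%, 28 are screened and 6 fail; the rows print 28/22 = 127.3% and 6/22 = 27.3%, against 6/28 = 21.4%.

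**Step 3: pre-screened row.** With s = 20%, 188 are screened. A 20% pre-screening loss means 235 pre-screened and a printed 235/150 = 156.7%. A 50% loss means 376 and 376/150 = 250.7%.

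**Step 4: enrolled but not treated.** If a proportion u of those enrolled is never dosed, the row prints u/(1-u). At an assumed u of 5% that is 0.05/0.95 = 5.3%, so the distortion here is small unless u is large.

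**Step 5: meaning of screen failure.** The readable text does not say whether CD30 failures at pre-screening count. In the 235-subject case, 47 are lost at pre-screening (235 - 188) and 38 at screening. The row prints 38/150 = 25.3% on the narrow reading and 85/150 = 56.7% on the broad one. The corresponding rates are 38/188 = 20.2% of screened and 85/235 = 36.2% of pre-screened.

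**The case against.** The strongest reply is that this is a table convention with little consequence. Counts are required beside the percentages, so any attrition rate is one division away. SAP 8.1 plans a listing of untreated subjects with reasons, and SAP 8.3 a listing of entry criteria violated at pre-screening and at screening. A printed value above 100% would be noticed at once. Table templates sit in a separate document (SAP 1), and parts of SAP 7 and 8.1 are not readable, so row-level denominators may be set there.

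Most of that stands, and it limits the importance of the point. It does not rescue the sentence in SAP 8.2, which is unqualified. Nothing readable overrides it, and a template that did so would conflict with the SAP. Nor is every wrong value self-evident: a screen-failure row reading 25% looks plausible when the true rate is 20%.

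A reader might infer more than the documents support:
- That all four rows exceed 100%. Only the pre-screened and screened rows must do so once anyone in them is untreated. The other two do so only if their counts outnumber the treated.
- That screening attrition cannot be known. It can be worked out from the printed counts.
- That everyone pre-screened and not treated is a screen failure. The two-stage process and the separate enrolled-but-not-treated row do not allow that to be assumed.

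**Conclusion.** The point holds as a reporting defect of minor weight. Followed as written, SAP 8.2 prints percentages on four rows that are not proportions of any group. The direction is certain from the definitions alone: the pre-screened and screened rows cannot fall below 100%, and the screen-failure row overstates the failure rate among those screened by the factor 1/(1-s) if all who pass are treated. The size depends on screening losses, which the documents do not give. Over assumed s of 10% to 60%, the failure row reads about 11% to 150%.

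It might be tempting to read this as touching the trial's conclusions. It does not: the response rates, their confidence intervals, the exact tests, the analysis sets and the sample size do not use these percentages.

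**What to change.** Replace the single-denominator sentence in SAP 8.2 with stage-specific denominators:
- number pre-screened, for the screened row and for any pre-screening (CD30) failures;
- number screened, for main-screening failures;
- number enrolled, for enrolled but not treated;
- FAS, for the analysis-set rows and every row from treatment start onward.

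Showing counts only on the pre-treatment rows is an acceptable alternative. Dividing main-screening failures by the number pre-screened is not, because it dilutes the rate with people who never entered screening.

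State whether the screen-failure row includes pre-screening failures, and preferably give the two kinds separate rows. Show the pre-screening rows at least overall: a PTCL patient with CD30 below 1% belongs to neither Cohort A nor Cohort B, so a by-cohort count would leave that patient out.

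The cost is a sentence or two in the SAP, a table footnote and a check that the template agrees. No new data are needed.
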